7 STATISTICAL METHODOLOGY

7.1 General Considerations

For continuous variables, descriptive statistics will include the number of subjects (n), mean, standard deviation, median, minimum and maximum. When needed, the use of other percentiles (e.g., 10%, 25%, 75% and 90%) will be specified in the relevant section. In addition, for plasma concentrations, the coefficient of variation and the geometric mean will also be calculated. Frequencies and percentages will be displayed for categorical data. Percentages by categories will be based on the number of subjects with no missing data, i.e., will add up to 100%.

SAP Final Version 4.0

Summaries based on ITT (e.g., disposition) will be presented by randomized treatment group, unless specifically stated otherwise. Safety analysis and other summaries based on SAF will be presented by actual treatment received. Pharmacokinetic summaries based on PKAS will be presented by actual treatment received. For subjects with dose increase/decrease, actual treatment refers to the initial dose received before dose change.

All statistical comparisons will be made using two-sided tests at the α =0.05 significance level unless specifically stated otherwise. All null hypotheses will be of no treatment difference, all alternative hypotheses will be two-sided, unless specifically stated otherwise.

All data processing, summarization, and analyses will be performed using SAS® Version 9.3 or higher on Statistical Computing Environment. Specifications for table, figure, and data listing formats can be found in the TLF specifications for this study.

Baseline is defined as the last available measurement prior to the first dose of study drug. Unless otherwise specified, all summaries will be presented by treatment groups.

For the definition of subgroups of interest please refer to Section 7.8.

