- i. Ophthalmologic assessment to be performed by visual acuity measurement and ophthalmoscopy during the screening period, day 1 (± 7 days) of cycle 2, day 1 (± 7 days) of every 2 cycles thereafter, and when clinically indicated. In symptomatic subjects, the ophthalmologic assessment should also include slit lamp biomicroscopy, visual fields performed by Humphrey method and optical coherence tomography.
- j. FLT3 mutation status will be assessed from bone marrow sample taken at the screening visit. If bone marrow sample is unavailable (e.g., dry tap), the whole blood sample taken at the screening visit will be used. Subjects must be screened by the central laboratory. All subjects including those with rapidly proliferative disease must have screening sample sent to the central lab. If central result is negative, central FLT3 testing can be repeated during screening period.
- k. Bone marrow samples are required during screening, cycle 2 day 1 and cycle 3 day 1. For subjects who do not achieve a CRc (CR, CRp or CRi), the bone marrow assessments will be repeated at day 1 of every 2 subsequent cycles. For subjects who achieve a CRc (CR, CRp or CRi), bone marrow sampling will be repeated on 1 month after the date of remission and every 3 subsequent cycles or if there is suspicion of relapse in the whole blood. Bone marrow samples are also required at the pre-HSCT visit/end of treatment visit and as clinically indicated. If bone marrow aspirate is unobtainable (e.g., dry tap), an additional EDTA tube of whole blood should be collected instead. Bone marrow aspirate is required, and bone marrow biopsy is preferred. In case of inadequate aspirate, bone marrow biopsy is required.
- 1. PK samples for ASP2215 will be collected on cycle 1 day 1 predose, cycle 1 day 8 predose and at cycle 1 day 15 and day 1 predose of each subsequent cycle (1 hour before drug administration). See Section 7.6 of the protocol.
- m. Whole blood and buccal swab collected at day 1 for optional pharmacogenomic study.
- n. ASP2215 is taken daily at home except for clinic days when it will be taken at the clinic.

Footnotes continued on next page

- o. Chest X-ray (or CT of chest) does not need to be repeated if performed within 2 weeks prior to start of screening.
- p. For the purposes of drug preparation and dispensing activities, IRT transaction may be done prior to the visit and do not need to fall within the protocol visit window.

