- The same analysis as primary analysis but with OS censoring at HSCT as defined in Section 6.1.1
- The same analysis as primary analysis but with OS censoring at first new antileukemia therapy as defined in Section 6.1.1
- Stratified Cox proportional hazard model with strata to control for response to firstline AML therapy and preselected salvage chemotherapy and initiation of new antileukemia therapy as a time-dependent binary covariate on ITT
- Additional sensitivity analysis will be performed using a new test for equality of two survival functions based on weighted differences of Kaplan–Meier curves with estimation of difference of Restricted Mean Survival Time (RMST) and its 95% CI (Uno et.al, 2015) by a pre-specified cutoff time at 18 months. The 18-month time-point was determined to ensure that reasonable number of patients were still at risk at the cutoff.
- The same analysis as primary analysis will be performed by dose adjustment for subjects whose dose was increased (200 mg dose), decreased (80 mg dose) or remained at 120 mg in ASP2215 arm.

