7.6 Analysis of PK

PK analysis will be conducted on the PKAS.

Plasma concentrations of ASP2215 will be summarized by treatment group and where appropriate by nominal time points using descriptive statistics, including number of subjects,

mean, standard deviation, minimum, median, maximum, geometric mean, and coefficient of variation (CV).

Population pharmacokinetic analysis will be performed. Data from this study may be pooled with other studies for analysis. Details of this analysis will be specified in a separate population pharmacokinetic analysis plan.

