7.11.2 Outliers

All values will be included in the analyses.

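### Later-cycle PK summaries pool samples taken at 80, 120 and 200 mg under the initial-dose group, with no split by dose at sampling

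*SAP*

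**What the plan says.** Two adjacent sentences in SAP section 7.1 (General Considerations) set the grouping. The first is "Pharmacokinetic summaries based on PKAS will be presented by actual treatment received". The second defines the term for anyone whose dose was changed: "For subjects with dose increase/decrease, actual treatment refers to the initial dose received before dose change".

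Section 7.6 (Analysis of PK) does not override this: "Plasma concentrations of ASP2215 will be summarized by treatment group and where appropriate by nominal time points using descriptive statistics". The statistics listed there include the mean, geometric mean and CV. No summary by dose at sampling, and no dose-normalised summary, is planned.

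Two other places show that this matters in the trial. The last OS sensitivity analysis in section 7.4.1 is for subjects "whose dose was increased (200 mg dose), decreased (80 mg dose) or remained at 120 mg in ASP2215 arm". The PK footnote to the ASP2215 schedule (section 2, Table 1) says "PK samples for ASP2215 will be collected on cycle 1 day 1 predose, cycle 1 day 8 predose and at cycle 1 day 15", and it continues predose sampling on day 1 of each later cycle.

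**The concern.** Concentration depends directly on dose. A subject moved to 200 mg or 80 mg still contributes samples at every later cycle, and the stated rule files those samples under the dose the subject started on. A later-cycle row can then hold three doses spanning a 2.5-fold range (200/80). The mix will vary from cycle to cycle as doses are changed and subjects leave treatment. A rise or fall in the tabulated geometric mean could reflect exposure at a constant dose, a shift in who is on which dose, or both. The table offers no way to separate them.

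The SAP treats dose as relevant elsewhere. It analyses OS (7.4.1), CR rate (7.4.3.1), CRc rate (7.4.3.2) and CR/CRh rate (7.4.6) by dose adjustment in the ASP2215 arm, but not plasma concentration.

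Plasma concentration is part of a stated secondary objective (3.1.2). Section 5 also lists the PKAS among the sets for the end-of-study report, although section 1 describes that analysis as covering safety data only.

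**Working it through.** There is no figure in the plan to reproduce, because the point concerns a grouping rule. The check first traces the rule and then illustrates its size.

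**Tracing the rule**

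1. PK summaries are grouped by actual treatment (7.1).
2. After an increase or decrease, actual treatment is the initial dose (7.1).
3. Within group, the only further split is nominal time (7.6).
4. Samples are taken predose on day 1 of every later cycle (Table 1, PK footnote), so sampling continues after dose changes.
5. Doses in the arm are 80, 120 and 200 mg (7.4.1). That 120 mg is the starting dose is inferred from 7.4.1 and from the 120 mg/day reference for relative dose intensity in 6.4.

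Samples taken after an increase or decrease are therefore summarised with the initial-dose group by a stated rule, not through an omission. The cycle 1 day 1 sample precedes the first dose and is unaffected.

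**Size**

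Assumptions that are not in the SAP: concentrations are proportional to dose; shares p200 and p80 of the samples in a row are at 200 and 80 mg; the rest are at 120 mg.

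Relative to 120 mg, the doses are 200/120 = 1.667 and 80/120 = 0.667, with logs 0.5108 and -0.4055.

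- Log geometric-mean ratio: M = 0.5108 p200 - 0.4055 p80. The ratio is exp(M).
- Variance of log dose: V = 0.5108² p200 + 0.4055² p80 - M² = 0.2609 p200 + 0.1644 p80 - M².
- CV from dose mixing alone: sqrt(exp(V) - 1).

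| 200 mg / 80 mg share | M | Geometric-mean ratio | V | CV from mixing |
|---|---|---|---|---|
| 10% / 5% | 0.0308 | 1.03 (+3%) | 0.0334 | 18% |
| 10% / 20% | -0.0300 | 0.97 (-3%) | 0.0581 | 24% |
| 30% / 10% | 0.1127 | 1.12 (+12%) | 0.0820 | 29% |
| 40% / 5% | 0.1841 | 1.20 (+20%) | 0.0787 | 29% |
| 40% / 20% | 0.1232 | 1.13 (+13%) | 0.1221 | 36% |

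Over 10-40% at 200 mg and 5-20% at 80 mg, the geometric-mean shift runs from -3% to +20% and the mixing CV from 18% to 36%.

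**With variability within dose**

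Add an assumed within-dose CV of 50%. With f the share of samples at each dose and r its ratio to 120 mg, the arithmetic mean ratio is m = Σ f r, and the pooled CV is sqrt(1.25 Σ f r² - m²)/m. For the 10%/20% mix:

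- m = 0.7 + 0.1 × 1.667 + 0.2 × 0.667 = 1.000
- Σ f r² = 0.7 + 0.2778 + 0.0889 = 1.0667
- CV = sqrt(1.3333 - 1) = 0.577

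The arithmetic mean looks exactly right while the CV rises from 50% to 58%. For 30%/10% the mean ratio is 1.17 and the CV 60%.

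**The case against.** With a single starting dose, the convention may do no more than keep one ASP2215 column. Concentrations in that arm as actually dosed are a legitimate description if labelled so. Table layouts are left to TLF specifications that are not shown, and no section prints a 120 mg label on a PK table. Population PK is to be performed under its own plan. Nothing inferential depends on these tables, and a by-dose table could be produced later from the data collected. Some plausible mixes move the geometric mean by only 2-3%.

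Most of this limits the point without removing it. The label is an inference, but the pooling occurs under any label. The ability to add a table later is a reason to specify it now.

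Three stronger readings are tempting, and the SAP does not support them.

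- **Interruptions.** The ECG footnote to Table 1 allows interruptions of up to 14 days, so a reader might infer that off-drug samples are pooled too. The 7.1 sentence covers only increases and decreases. The PKAS definition (5.4) requires a known dosing date and time on the sampling day, and it leaves time-point exclusions to the Classification Specifications, which are not shown. The SAP does not settle how such samples are handled.
- **Outlier rule.** "All values will be included in the analyses" (7.11.2) might be read as keeping every sample in the summary. It concerns outliers, does not govern dose grouping, and sits alongside the exclusions allowed in 5.4.
- **No usable exposure estimate.** A reader might conclude that the trial will yield no exposure estimate at a single dose, or that the tables are meaningless. The population PK plan is not shown and cannot be judged, and a diluted summary is not an empty one.

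**Conclusion.** The point stands as a moderate defect in a descriptive analysis. Under 7.1 and 7.6, concentrations sampled after a dose increase or decrease are summarised under the initial dose, so later-cycle means, geometric means and CVs mix doses, and their trend over cycles cannot be read as exposure at a constant dose. The conclusion about grouping follows from the text alone.

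The size does not. The range of -3% to +20% for the geometric mean and 18-36% for the mixing CV rests on assumed dose proportionality and assumed dose shares. With an assumed 50% within-dose CV, the pooled CV is about 51-62% for mixes of up to 40% at 200 mg and up to 20% at 80 mg. The effect is confined to descriptive PK tables and graphs. No hypothesis test, alpha allocation or sample size changes.

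**What to change.** In 7.1, limit the initial-dose convention to safety summaries. In 7.6, summarise plasma concentrations by nominal time and by the dose actually taken before the sample, using the dosing CRF. An acceptable alternative is to restrict the initial-dose summary to samples taken before any dose change and to say so in the table title. If the dose cells are small, add a dose-normalised summary with its proportionality assumption stated.

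The cost is a sentence or two in the SAP and a by-dose split in the tables. ASP2215 dose with start and stop dates is already on the dosing CRF (6.4), and the PKAS already requires known sampling times (5.4). The downside is small numbers in the 80 and 200 mg cells at late cycles. The change concerns analysis grouping only and implies nothing about dosing.

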7.2 Study Population

7.2.1 Disposition of Subjects

The following subject data will be presented:

- Number and percentage of subjects with informed consent, re-screening, discontinued before randomization, randomized (overall only);
- Number and percentage of subjects randomized in each analysis set, by treatment group and overall;
- Number and percentage of subjects completed and discontinued treatment, by primary reason for treatment discontinuation for randomized subjects, by treatment group;
- Number and percentage of subjects completed the 30-day follow-up evaluation, by 30-day follow-up status for randomized subjects and by treatment group;
- Number and percentage of subjects completed the long term follow-up evaluation, by long term follow-up status for randomized subjects and by treatment group.

7.2.2 Protocol Deviations

Protocol deviations as defined in the study protocol (Section 8.1.6 Protocol Deviations) will be assessed for all randomized subjects. The number and percentage of subjects meeting any criteria will be summarized for each criterion and overall, by treatment group and total as well as by study site. Subjects deviating from a criterion more than once will be counted once for the corresponding criterion. Any subjects who have more than one protocol deviation will be counted once in the overall summary. A data listing will be provided by site and subject.

The protocol deviation criteria will be uniquely identified in the summary table and listing. The unique identifiers will be as follows:

- PD1 Entered into the study even though they did not satisfy entry criteria,
- PD2 Developed withdrawal criteria during the study and was not withdrawn,
- PD3 Received wrong treatment or incorrect dose,
- PD4 Received excluded concomitant treatment.

The visit-based assessments affected by COVID-19 pandemic such as the assessments performed out of window, performed at alternative location or virtual assessment due to COVID-19 will be provided in data listings by site and subject.

The non-visit-based assessments affected by COVID-19 pandemic such as treatment discontinuation, adverse event, dose changes due to COVID-19 will be provided in data listings by site and subject.

7.2.3 Demographic and Other Baseline Characteristics

The demographics and other baseline characteristics were reported in the primary CSR dated 24 JAN 2019 for the data with cutoff date of 17 SEP 2018. Those will not be summarized for the end of study report.

Demographic and other baseline characteristics will be summarized by descriptive statistics.

Number and percentage of subjects allocated to treatment in each country and site will be presented by treatment group.

Descriptive statistics for age, weight, body surface area (BSA) and height at study entry will be presented by treatment group. Frequency tabulations for sex, ethnicity, age group (defined in Section 7.8), race, region, baseline central FLT3 status, baseline ECOG, prior use of FLT3 inhibitor and cytogenetic risk status will be presented by treatment group.

Frequency tabulations for AML disease history including AML subtype as classified by World Health Organization (WHO) classification and French-American-British (FAB) classification, risk status, antecedent hematological disorder, central nervous system leukemia, rapidly progressing disease, local FLT3 mutation status, local FLT3-ITD mutation status, local FLT3 point mutation status will be presented by treatment group.

Medical history other than AML and conditions existing at Baseline will be coded in MedDRA and summarized by System Organ Class (SOC) and Preferred Term (PT) as well as

by PT alone, by treatment group. Baseline conditions are defined as those ongoing at the time of informed consent or arise following the time of informed consent and before the first dose of study drug. For ongoing medical conditions, Common Terminology Criteria for Adverse Events (CTCAE) grade will be provided in listing.

Frequency tabulations for prior transplant including number of prior transplant, graft type, donor relatedness, match type and outcome of transplant will be presented by treatment group.

Results from lumbar puncture, baseline extramedullary leukemia and MUGA scan, if performed, will be provided in listing.

7.2.4 Previous and Concomitant Medications

The prior medications were reported in the primary CSR dated 24 JAN 2019 for the data with cutoff date of 17 SEP 2018. Only concomitant medications will be summarized for the end of study report.

Previous medications are coded with World Health Organization – Drug Dictionary (WHO-DD), and will be summarized by therapeutic subgroup (Anatomical Therapeutic Chemical [ATC] 2nd level) and chemical subgroup (ATC 4th level) and preferred WHO name by treatment group.

As with previous medication, concomitant medication will be summarized for each treatment group by therapeutic subgroup (ATC 2nd level) and chemical subgroup (ATC 4th level) and preferred WHO name for the SAF. Subjects taking the same medication multiple times will be counted once per medication and investigational period. A medication which can be classified into several chemical and/or therapeutic subgroups is presented in all chemical and therapeutic subgroups.

Concomitant medication will also be summarized by treatment group and PT and presented in decreasing order of frequency based on the total number of subjects took each medication.

7.2.5 Previous and Concomitant Transfusions

The prior transfusions were reported in the primary CSR dated 24 JAN 2019 for the data with cutoff date of 17 SEP 2018. Only concomitant transfusions will be summarized for the end of study report.

Frequency tabulations of subjects received transfusions and blood product will be presented for previous transfusion and concomitant transfusion by treatment group Descriptive statistics will be presented for number of transfusion unit received per subject for each type of blood product.

7.2.6 Prior AML Chemotherapy

The prior AML chemotherapy was reported in the primary CSR dated 24 JAN 2019 for the data with cutoff date of 17 SEP 2018. This data will not be summarized for the end of study report.

Frequency tabulations of subjects with prior AML chemotherapy, response to first line therapy, regimen, type of treatment, prior use of FLT3 inhibitor, and best response to prior AML therapy will be presented by treatment group. Descriptive statistics will be presented for duration of response to prior AML therapy.

7.2.7 Non-Medication Therapy

Frequency tabulations of subjects with non-medication therapy and reason for use will be presented by treatment group. Number of non-medication therapy received per subject will be summarized using descriptive statistics.

7.2.8 Clinical/Diagnostic Procedures

Frequency tabulations of subjects with clinical/diagnostic procedures and reason for use will be presented by treatment group. Number of clinical/diagnostic procedures received per subject will be summarized using descriptive statistics.

7.2.9 Subsequent AML Therapy

Frequency tabulations of subjects with subsequent AML therapy, regimens, relapse prior to subsequent AML therapy, reason of starting subsequent AML therapy, and response to subsequent AML treatment will be presented by treatment group. Descriptive statistics will be presented for duration of subsequent AML therapy.

7.3 Study Drugs

7.3.1 Exposure

The following information on drug exposure will be presented for each treatment regimen for the SAF:

- Descriptive statistics for cumulative amount of the drug subject was exposed to, number
 of dosing days, number of dosing cycles, average daily dose, dose intensity, and relative
 dose intensity; and
- Number and percent of subject with dose increases, decreases or interruptions.

Duration of exposure will be summarized in two ways.

- Descriptive statistics will be presented by treatment regimen.
- Exposure time will be categorized according to the following categories by treatment regimen:
 - o less than or equal to 5 days
 - o at least 6 days, less than 28 days
 - o at least 28 days, less than 84 days
 - o at least 84 days, less than 168 days
 - o 168 days or more
 - o Unknown.

Counts and percentages of subjects in each of these categories will be summarized for each treatment regimen for the SAF.

Listing of subjects with dose reduction and dose escalation will also be provided.

7.4 Analysis of Efficacy

There will be no efficacy analysis performed for the end of study report.

The significance levels at each interim and final analyses for each co-primary and secondary endpoints are specified in Table 4 below:

Table 4 Summary of Timing, Sample Size and Decision Guidance at the Planned Analyses

Analysis	Criteria for	Endpoint/	Efficacy B	Soundary*	Futility B	oundary*
	conduct of analysis (Projected timing)	Analysis Set	p-value (1-sided) at the Boundary	Approx. Observed HR at Boundary	p-value (1-sided) at the Boundary	Approx. Observed HR at Boundary
First Interim Analysis: CR/CRh rate	When 141 subjects are randomized into ASP2215 arm and at least 112 days (4 treatment cycles) post first dose or randomization (for subjects who received no study drug)	CR/CRh rate /2215 subjects in RAS	NA (0.0005 nominal)	NA	NA	NA
Second Interim	Approx. 129 OS	OS/ITT	0.00147	0.57	0.38674	0.95
Analysis:	events were observed	EFS/ITT	0.01519	0.67	0.30218	0.91
OS; EFS when null hypothesis of OS is rejected; CR rate when null hypotheses of both EFS and OS are rejected	Observed	CR rate/ITT	0.01519	NA	0.30218	NA
Final Analysis:	Approx. 258 OS	OS/ITT	0.02402	0.77	NA	NA
OS; EFS when	events were observed	EFS/ITT	0.01357	0.75	NA	NA
null hypothesis of OS is rejected; CR rate when null hypotheses of both EFS and OS are rejected	observed	CR rate/ITT	0.01357	NA	NA	NA

^{*:} P-value at both efficacy and futility boundaries (except the first interim) are based on 50% information fraction for OS, EFS and CR rate, and need update based on actual observed number of events at the second interim and final analysis.

